#### *Near- infrared spectroscopy (NIRS)*

Muscle oxygenation in the microcirculation of the *m. vastus lateralis* will be measured using a commercially available NIRS system (Portamon, Artinis, Netherlands) during the pre- and post-immersion periods. This system is non-invasive and will be placed on *m. vastus lateralis* of the right leg. NIRS is used to estimate changes, relative to baseline, in oxygenated and deoxygenated haemoglobin concentrations, myoglobin concentrations, total haemoglobin and tissue saturation index to give an insight into the dynamic balance between muscle  $O_2$  delivery and utilisation. Furthermore, a skin-fold measurement at the site in which the NIRS device is fixed will be recorded, in line with the manufacturer's recommendations.

#### *HR and BP*

HR will be automatically calculated from the ECG, real-time. Blood pressure will be measured every 30 min via a patient monitor brachial BP cuff (Dynascope, Fukuda Denshi, Japan).

#### *HRV*

HRV will be calculated as a low frequency (LF) variable and root mean square of successive differences (RMSSD). LF has been chosen as it indicates a physiological origin of both sympathetic and vagal activity. RMSSD is then being calculated additionally as it gives a stronger representation of vagal tone (due to it being affected much less by respiratory sinus

arrhythmia (RSA)) than LF thus improving validity of the vagal tone measure [Laborde et al., 2017]. Both measures will be calculated from an ECG trace.

### *Biochemistry*

Venous blood samples will be collected via cannulas (ideally located in the Cephalic vein on the forearm, alternatively either in hand or antecubital fossa. All locations will out of the water at all times) into fluoride, LH and EDTA vacutainers during all visits. All whole blood will be centrifuged at 4500 x g for 10 mins, at 4 °C and aliquoted plasma will be frozen at -80 °C for subsequent analysis.

Plasma [glucose] will be determined by the Department of Biochemistry at the Queens Alexandra Hospital, Portsmouth. Commercially available enzyme-linked immunosorbent assays will be used to determine [insulin], [IL-6], [IL-10] and [eHSP70]. Haemoglobin and haematocrit will be measured via Haemacue (Hb 201, Sweden) and capillary tubes (Microhaematocrit capillary tubes, Hawksley, UK) respectively at all data collection time points in triplicate.

### *Follow-up questions*

A few semi-structure follow-up questions will be given to the participants to get feedback on how they felt in the hot water in both conditions. The questions will be related to how they felt in terms of heat tolerance, lethargy, well-being and also how they felt in the hours and days following each visit.

## **9.5 Discontinuation/Withdrawal of Participants from Study Treatment**

Participants may be withdrawn from the study if they ask to withdraw, if participant safety is in question or if the study is stopped early.

## **9.6 Definition of End of Study**

The end of study will be following the final dissemination of results, which is expected to be during September 2019.

# **10. INTERVENTIONS**

## **10.1 Description of Study Intervention / Treatment**

The passive heating condition will be conducted in a thermoneutral room (~ 23°C air, ~ 90% RH) with the heating taking place for 60 min in a heated pool (starting at 39°C water (~ 90% RH) and then cooling to clamp  $T_{rec}$  at 38.5°C). The participant will firstly be cannulated, lie horizontal and baseline measures taken after 15 min rest period. Following baseline measures an OGTT will start. Thirty min into the OGTT, the passive heating will start with the participant entering the pool and lying horizontally on a submerged bed with their head and neck elevated

above the water. Participants' rectal temperature ( $T_{\text{rec}}$ ) will be monitored so that once it reaches  $38^{\circ}\text{C}$  the water will be cooled slightly to arrest the rise in  $T_{\text{rec}}$  and maintain  $T_{\text{rec}}$  at  $38.5^{\circ}\text{C}$  ( $T_{\text{rec}}$  is still expected to rise slightly after reduction in water temperature, see below for more details). If  $T_{\text{rec}}$  at any point reaches  $39^{\circ}\text{C}$  or above, the participant will immediately be withdrawn from the study and a cooling protocol administered (see SOP attached). Passive heating will cease by winching the participant out of the pool and onto the dry bed with the participant still lying in a semi-recumbent position. The participant will then be dried and given a blanket (to ensure heat retention as would be the case with putting on clothing after bathing) and remain semi-recumbent until completion of the visit. The remainder of the OGTT will be conducted in the thermoneutral room ( $\sim 23^{\circ}\text{C}$  room temperature).

Core temperature ( $T_{\text{rec}}$ ) will be measured continuously throughout each visit using disposable rectal thermistors (which will be checked for accuracy in a water bath prior to each trial  $\pm 0.2^{\circ}\text{C}$ ). Participants will insert the thermistor 15 cm (this will be marked with sterilised tape) into the rectum using standard operating procedures.  $T_{\text{rec}}$  will be closely monitored throughout the passive heating condition to ensure that it does not exceed  $39^{\circ}\text{C}$ . For analysis, data will be grouped into 1 min average intervals (and will be collected at a 1 Hz sampling frequency).

### 10.2 Adherence to Study Treatment

Participants will be immersed into the pool and core temperature measured to ensure safety. Participants can, at any time, ask to be safely removed from the pool. Additionally, participant will be removed from the pool if  $T_{\text{rec}}$  reaches  $>39^{\circ}\text{C}$ . Total time in the pool will be calculated for each participant on each visit.

### 10.3 Accountability of the Study Treatment

**Any of the study investigators are able to be accountable for maintaining the appropriate water temperature.**

### 10.4 Concomitant Medication / Therapies

Participant involvement is anticipated to be 3 morning sessions within a period of  $\sim 3$  weeks. Medication will be recorded on enrolment and updated throughout their time on the trial. For each experimental visit, hypoglycaemic aids will be stopped for the morning (see pre experimental instructions for details).

## 11. ASSESSMENT OF SAFETY

### 11.1 Definitions

A serious adverse event (SAE) is any untoward medical occurrence that:

- Results in death
- Is life-threatening\*

\*The term "life-threatening" refers to an event in which the participant was at risk of death; it does not refer to an event which hypothetically might have caused death if it were more severe.

- Requires inpatient hospitalisation or prolongation of existing hospitalisation
- Results in persistent or significant disability/incapacity
- Is a congenital anomaly/birth defect
- Other important medical events\*

\*Other events that may not result in death, are not life threatening or do not require hospitalisation may be considered a SAE when, based upon appropriate medical judgement, the event may jeopardise the participant and may require medical or surgical intervention to prevent one of the outcomes listed above.

### **11.2 Reporting Procedures for Serious Adverse Events**

SAE occurring to participant should be reported to the research ethics committee (REC) that gave a favourable opinion of the study where in the opinion of the Chief Investigator the event was: 'related' – that is, it resulted from administration of any of the research procedures; and 'unexpected' – that is, the type of event is not listed in the protocol as an expected occurrence. Reports of related and unexpected SAEs should be submitted within 15 days of the Chief Investigator becoming aware of the event, using the national research ethics service (NRES) report of serious adverse event form (see NRES website).

### **11.3 Recording and Reporting Procedures for All Adverse Events**

All adverse events will be recorded in participant file notes. Distinction between SAE and adverse event (AE) will be made by an independent medical officer. All SAE will be reported to the sponsor and the REC regardless of if it is related or not.

## **12. DATA HANDLING AND RECORD KEEPING**

### **12.1 Data Collection Forms**

Visit 1 will act as a screening and consent (ECG checked by clinical physician and blood to be analysed for a full blood count, HbA1c, estimated glomerular filtration rate (eGFR) and liver function). All measures for this visit will be stored in the clinical records folder (CRF). Separate forms will be prepared for; anthropometrics, medical history, screening (i.e. blood pressures etc) and blood markers. On subsequent visits data forms will be used to collect temperatures of the labs and immersion pool. All paper copies will be stored in the CRF's.

### **12.2 Data Management**

All data will be double data entered into excel. Macro's will be used to check for anomalies and corrected. The participants will be identified by a study specific participants number and/or code in any database. The name and any other identifying detail will not be included in any

study data electronic file. The Chief and Principal Investigators are responsible for database maintenance and management.

## **13. DATA ANALYSIS**

### **13.1 Description of Analysis Populations**

Participants who completed all 4 visits will be entered into the analysis.

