#### Exclusion Criteria

The participant may not enter / be withdrawn from the study if ANY of the following apply:

- Severe peripheral neuropathy (to the point to which they cannot sense temperature)
- Uncontrolled hypertension ( $\geq 180$  systolic / 100 diastolic mmHg)
- Taking any medication which may interfere with data interpretation or safety
- Who have had a myocardial infarction or cerebro-vascular event
- Any cardiac abnormalities which restrict hard exercise
- Current smokers or who have stopped within 3 months
- Participant is unable to understand and/or fully cooperate with the study protocol

- Any other serious medical condition which would interfere with data interpretation or safety will be excluded from participation.
- Any skin conditions including ulcerations

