#### *Passive heating and Core Temp*

The passive heating conditions (conditions 2 and 3) will be conducted in a thermoneutral room (~ 23°C air, ~ 90% RH), at the same time of day, with the heating taking place for 60 min in a heated pool (starting at 39°C water). Pre and post body mass will also be recorded, along with any fluid or solids going into or out of the body. Participants will firstly be cannulated lying horizontal, then will lie semi-recumbent and baseline measures taken. Depending on which condition (either 2 or 3) the OGTT or the passive heating will start first. Passive heating will start with the participant entering the pool and lying semi-recumbent on a submerged bed with their head, neck and cannulated arm above the water. Participants' rectal temperature ( $T_{rec}$ ) will be monitored so that once it reaches ~38°C the water will be cooled to ~ 38 - 38.5°C so that it will maintain  $T_{rec}$  at ~ 38.5°C ( $T_{rec}$  is still expected to rise slightly after reduction in water temperature, see below for more details). If  $T_{rec}$  reaches 39°C or above at any point, the participant will immediately be withdrawn from the study and a cooling protocol administered (see SOP attached). Additionally, if systolic BP raises above 180 mmHg or HR above 140

bpm, participants will be immediately withdrawn from the study. Passive heating will cease by winching the participant, still lying semi-recumbent, out of the immersion tank and onto a semi-recumbent bed. The participant will then be towel dried and given a blanket (to ensure maximum heat retention) and remain semi-recumbent until completion of the visit. The remainder of the visit will be conducted in the thermoneutral room.

$T_{rec}$  will be measured continuously throughout each visit using disposable rectal thermistors (Rectal temperature probe, Philips, Netherlands). Participants will self-insert the thermistor to 15 cm (this will be marked with sterilised tape) into the rectum using standard operating procedures.  $T_{rec}$  will be closely monitored throughout the passive heating conditions to ensure that it does not exceed 39°C.

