## **14. ETHICS**

NHS Local Research Ethics Committee (REC) approval will be obtained prior to commencement of the study. The REC, local NHS, research and development department and all site specific forms and patient identification centre forms will be forwarded to the R&D department at Queen Alexandra Hospital Portsmouth, prior to recruitment of participants. Written informed consent will be obtained from all participants. Insurance indemnity will be provided by the University of Portsmouth for this study.

Every effort has been made to keep the risks and discomforts to a minimum, with first aid cover and extensive screening procedures in place but there are some risks associated to taking part. Not all volunteers will experience any or all of the risks stated below, but participants will be made aware of them.

The main burden to participants is a 12 h fasting period before their visit. Participants will be asked to cease all hypoglycaemic agents on the morning of testing and will be instructed to bring them with them on the day. This is in line with a normal fasted OGTT typically used in clinics. Prior to leaving the laboratory, participants will be provided with lunch, they can take their tablets and blood sugars checked prior to leaving.

We will also be asking people with T2DM to be submerged in hot water for condition 2 and 3. This may cause some discomfort which will be assessed with a thermal sensation and comfort scale. We will be measuring the core temperature via rectal thermistor and monitoring it closely at all times. Participants will be reminded that they are free to withdraw at any time point and will also be withdrawn and cooled if  $T_{rec}$  raises above 39°C (as stated in the departments SAP's).

Participants will be asked to insert a rectal thermistor on two out of the four visits (water immersions). This can be uncomfortable upon insertion; however, this is necessary for safety purposes. Participants will be provided with lubrication and instructions.

Other less burdensome tests will be performed such as:

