Blood pressure; participants will feel a cuff squeeze their arm and this can be uncomfortable for a few moments. Blood samples taken every 30min via cannulation (using the appropriate hygienic technique and by a trained individual): Intravenous access can cause discomfort associated with insertion of the needle. Infusion of saline (5 mL.30min) will be applied to minimise infection risk (flushing and locking eliminates potential nesting sites for microorganisms) and clotting. To avoid the saline affecting subsequent samples, 2.5 mL of blood will be drawn from the cannula before they are collected.

Other risks that have been accounted for are hypotension and loss of consciousness in the water. If at any point the participants BP is measured at  $\geq 180/100$  the trial will be terminated and the participant withdrawn from the study. If there is loss of consciousness in the water the participant will immediately be harnessed securely out. This can be done quickly as they will already be lying on the sling. Once they are out of the water and placed on a bed, their breathing will be checked and first aid administered. They will also be cooled via cold water spray and a fan. Additionally, their head will never go underwater as their head will be elevated above waterline throughout all submersions.

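### Section 13.1 analyses four-visit completers only: any withdrawal at a limit during a heated visit makes inclusion depend partly on response to the heat and discards that person's completed visits

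*Combined protocol and SAP*

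**What the plan says.** - **Analysis set.** Section 13.1 is a single rule: "Participants who completed all 4 visits will be entered into the analysis". Visit 1 is screening, and visits 2 to 4 are the three conditions, two of them heated (section 6.3). No all-randomised set, available-data set or sensitivity analysis is defined.
- **Temperature limit.** In section 9.4 (Passive heating and Core Temp), at a rectal temperature of 39°C or above, "the participant will immediately be withdrawn from the study and a cooling protocol administered". Section 10.1 repeats this for 39°C "or above, the participant will immediately be withdrawn from the study and a cooling protocol administered". Section 14 says participants are "free to withdraw at any time point and will also be withdrawn and cooled if" it rises above 39°C, without saying what they are withdrawn from. Section 10.2 mentions only removal from the pool above 39°C.
- **Blood pressure and heart rate limits.** Section 9.4 also withdraws participants from the study "if systolic BP raises above 180 mmHg or HR above 140" bpm. Section 14 says that at a blood pressure of 180/100 or more, at any point, "the trial will be terminated and the participant withdrawn from the study".
- **What happens to the data.** Section 9.5 lists reasons for withdrawal but not the fate of the data. Section 13.3 skips missing data points. Section 10.2 records pool time and lets participants ask to come out, but does not say whether a shortened immersion makes a completed visit. Section 13.2 plans a one-way ANOVA across conditions.
- **Features that limit the problem.** Once rectal temperature is about 38°C, "the water will be cooled to ~ 38 - 38.5°C so that it will maintain" it near 38.5°C (section 9.4). The exclusion list in section 7.3 is headed as applying to anyone who "may not enter / be withdrawn from the study if ANY of the following apply", and it includes the same 180/100 limit, which can be met without heat.

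**The concern.** In a crossover, each person should contribute whatever conditions they provided, and membership of the analysis set should not depend on what happens under treatment. Here it can. A person withdrawn during an immersion cannot complete four visits, so section 13.1 removes them, including any control or heated OGTT already done. Section 13.3 works on data points within included participants and does not bring that person back.

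If such withdrawals occur, the estimate describes people able to complete both immersions but would be reported as the effect in people with T2DM. Section 8 plans to use the resulting effect sizes to power later trials, so the selection would carry forward.

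**Working it through.** **1. The plan's own figures.** Section 8 gives 13 participants for 90% power at a 1 SD within-person difference (two-sided 0.05), 18 completers for counterbalancing and 20 recruited for 10% drop-out. A paired t-test with noncentral t gives power 0.883 at n = 12 and 0.911 at n = 13, so 13 reproduces. 18/(1 − 0.10) = 20 also reproduces. Power is 0.979 at 18 and 0.989 at 20. The stated power is not what is at risk.

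**2. Completed visits lost with each withdrawal.** Write C for control and A, B for the heated conditions, with six equally likely orders.

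| Order | Done before 1st immersion | Done before 2nd immersion |
|---|---|---|
| CAB | C | C, A |
| CBA | C | C, B |
| ACB | none | A, C |
| BCA | none | B, C |
| ABC | none | A |
| BAC | none | B |
| Mean number | 2/6 = 1/3 | 10/6 = 5/3 |

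For two such participants, out of 20 × 3 = 60 planned experimental visits, 2 × 1/3 = 0.7 completed visits are discarded if they stop at the first immersion and 2 × 5/3 = 3.3 if at the second. In four of the six orders, a person lost at the first immersion has no completed experimental visit.

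**3. Shift in the completers' mean.** The documents give no correlation *r* between thermal strain and glucose response and no rate of heat-related withdrawal. I assume *r* = 0.3 to 0.5 and loss of the most strained 1 or 2 of 20. The expected two largest of 20 standard normal values are 1.867 and 1.408.

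- Lose one: 1.867/19 = 0.098; times 0.3 to 0.5 gives 0.03 to 0.05 SD.
- Lose two: (1.867 + 1.408)/18 = 0.182; times 0.3 to 0.5 gives 0.05 to 0.09 SD.
- If no loss is heat-related, or *r* = 0, the shift is zero.

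The unit is the SD of individual response. The direction depends on the sign of *r*, which is unknown.

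**4. Against sampling error.** At 18 completers the standard error is 1/√18 = 0.236 SD. Taking the SD of individual response as equal to the SD of the paired difference (an upper bound), the two-loss shift is 0.055/0.236 = 0.23 to 0.091/0.236 = 0.39 standard errors. Coverage of the nominal 95% interval (noncentral t, 17 df) falls to about 0.945 and 0.935.

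**5. Information recovered by using every visit.** Variance of one heated-minus-control contrast from 18 completers, divided by that from 18 completers plus 2 partial participants, by generalised least squares with within-person correlation ρ (assumed):

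| Visits the two partial participants have | ρ = 0.5 | ρ = 0.8 |
|---|---|---|
| Control and the same heated condition | 1.111 | 1.111 |
| Control and the other heated condition | 1.034 | 1.029 |
| Control only | 1.026 | 1.010 |
| Other heated condition only | 1.000 | 1.000 |

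The gain is 0 to 11%.

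**6. Bias removed by using every visit.** Simulation with compound symmetry, ρ = 0.5 and 0.8, *r* = 0.3 to 0.5, top 2 of 20 lost, 20,000 trials per setting:

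| Loss occurs at | Completers only | All available visits |
|---|---|---|
| First immersion | 0.055–0.091 SD | 0.055–0.091 SD |
| Second immersion | 0.055–0.091 SD | 0.026–0.042 SD |

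Using all visits roughly halves the shift for loss at the second immersion and does essentially nothing for loss at the first.

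**The case against.** **The bias is small and may not exist.** Even with both losses heat-driven and falling on the two most strained people, the shift is at most 0.39 standard errors. The 10% in section 8 is general drop-out, not withdrawal at a limit, and *r* has no source in the documents. This stands: the point is modest.

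**The design works against the trigger.** Section 6.3 keeps the water between 37.5 and 39°C, so its maximum equals the rectal temperature limit. Cooling starts at about 38°C and exposure is 60 minutes. Section 7.3 excludes prior infarction or stroke and cardiac abnormalities that restrict hard exercise, and a consultant reviews the ECG. This makes a withdrawal less likely but does not close the route: the target is 0.5°C below the limit, sections 9.4 and 10.1 expect some further rise after cooling, and heart rate and blood pressure limits apply as well.

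**The remedy misses much of the problem.** A mixed model leaves loss at the first immersion uncorrected, and that may be the likelier pattern if heat susceptibility is a stable trait. Its missing-at-random assumption is doubtful here. This stands, and is why the fix also needs reporting of withdrawals and a limit on the conclusion.

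**A completer estimate can be defended.** If later trials keep similar limits, the effect in people able to finish is a relevant input. That is fair if the estimate is labelled so; section 13.1 does not label it.

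**The premise depends on an unresolved conflict.** If section 10.2 (removal from the pool only) governed, a person could still finish four visits and be analysed. Sections 9.4 and 10.1 say otherwise. The conflict is a separate documentation matter and adds no weight to this point.

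**Conclusion.** The concern holds as a conditional statement. Section 13.1 admits only four-visit completers, sections 9.4, 10.1 and 14 withdraw people from the study at limits that heating can trigger, and nothing in sections 9.5, 10.2 or 13.3 restores those people or their completed visits.

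The illustrated shift is 0.03 to 0.05 SD for one heat-related loss and 0.05 to 0.09 SD for two. It is zero if no loss is heat-related or if strain is unrelated to glucose response. These figures rest on assumed correlations and losses; the documents supply neither a rate nor a direction. Power is not materially affected. The change should be made because it costs almost nothing and the rule on who is analysed ought to be fixed before data are seen, not because a large bias has been shown.

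**What to change.** - **Section 13.1.** Make the primary set all randomised participants with at least one evaluable OGTT AUC, analysed by assigned condition. Keep four-visit completers as a sensitivity analysis.
- **Section 13.2.** Replace the ANOVA for AUC with a mixed model: condition and period as fixed effects, participant as random effect, every available visit used. This matching line is needed because a repeated-measures ANOVA drops anyone missing a condition.
- **Evaluable visit.** State whether a visit with a shortened immersion counts, using the pool time that section 10.2 already records. Say also what AUC is used when a visit stops early. By section 6.3, immersion in condition 2 runs from 30 to 90 minutes of the OGTT, so stopping the visit there can leave a partial curve. In condition 3 immersion precedes the OGTT, so stopping the visit there leaves none.
- **Reporting.** Tabulate withdrawals by condition, visit and reason. If any are heat-related, limit the conclusion to people able to complete the immersions.
- **Separately.** Sections 7.3, 9.4, 10.1, 10.2 and 14 must be reconciled on the limits and on whether reaching one ends the immersion or study participation. Which rule is right is for the study team.

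The analysis change is wording in sections 13.1 and 13.2, with no extra visits or samples. The downside is reliance on missing at random, which heat-driven withdrawal may violate. The model recovers data already collected and reduces bias for loss at the second immersion, but does not remove it for loss at the first.

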#### Visit 1 (consent, screening and familiarisation)

During visit 1, participants will give their informed consent, followed by a health screening questionnaire. In addition to the health screening questionnaire, medical history and a blood sample will be collected and analysed for a full blood count, glycated haemoglobin (HbA1c), liver and kidney function. Finally, a resting electrocardiogram (ECG) will also be recorded and then examined for irregularities, where a clinical decision will be made on further participation to the study by consultants at QA hospital. Participants will then be shown the rest of the equipment and taken through the procedure for the next 3 visits and, if the participant is happy to continue the study, the next visit will be organised.

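### The only analysis set is completers of all four visits, so people withdrawn at a temperature, heart rate or blood pressure limit are largely left out, and Section 13 plans no summary that includes them

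*Combined protocol and SAP*

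**What the plan says.** Section 13.1 gives the whole definition of the analysis population in one sentence: "Participants who completed all 4 visits will be entered into the analysis". No safety set or all-starters set is defined.

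The withdrawal rules are spread over three sections:

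- **Temperature.** In Section 9.4 (Passive heating and Core Temp), at a rectal temperature of 39°C or more, "the participant will immediately be withdrawn from the study and a cooling protocol administered". Section 10.1 repeats this, and Section 14 says that participants "will also be withdrawn and cooled if" temperature goes above 39°C.
- **Heart rate and systolic pressure.** Section 9.4 requires immediate withdrawal from the study "if systolic BP raises above 180 mmHg or HR above 140" beats per minute.
- **Blood pressure.** Section 14 says that at 180/100 or above "the trial will be terminated and the participant withdrawn from the study".

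Section 10.2 is softer. Above 39°C it requires removal from the pool and does not mention leaving the study. It also lets participants leave the pool on request, and it has pool time calculated for each person and visit.

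Section 13.2 lists glucose, insulin, insulin sensitivity, eHSP70, IL-6, IL-10, HRV, NIRS and RMR. It does not list adverse events, stopped immersions, withdrawals, heart rate or blood pressure, although the Synopsis names the last two as secondary endpoints. Section 13.4 says that nothing beyond Section 13 is needed as an analysis plan.

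**The concern.** The withdrawal rules and the analysis set act on the same people. Someone in whom the bath drove temperature, heart rate or pressure to a limit is taken out of the study, and 13.1 then takes that person out of the analysis, including data from visits already finished. If heart rate and blood pressure are analysed in that set, they are analysed in people selected for not having reached the limits.

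Two uses of the results are at stake. The Synopsis presents the bath as a possible low-cost therapy, so a reader will want to know how often it had to be stopped. Section 19 plans to use the results to power a larger study. That section does not mention stopping rates, but this trial's own sample size (Section 8) uses a drop-out rate, and its successor will need one too. Without a count by reason, losses caused by the bath cannot be told apart from other losses.

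**Working it through.** **1. The plan's own figures (Section 8).** The inputs are a difference of 1 SD, two-sided alpha 0.05, 90% power, 18 completers and 10% drop-out. I take the 1 SD as the SD of the within-person difference. Paired t-test power then comes from the noncentral t with n − 1 degrees of freedom and noncentrality √n. It is 0.883 for n = 12 and 0.911 for n = 13, so 13 reproduces. Recruitment is 18 / (1 − 0.10) = 20, which also reproduces. These figures are sound and are not in question.

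**2. Who falls out of the set.** This follows from reading 13.1 with 9.4, 10.1 and 14.

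- *Limit reached at visit 2 or 3:* the person is withdrawn, cannot attend the remaining visits, and is excluded.
- *Limit first reached at visit 4:* the person has attended every visit but is withdrawn during the last. Completion is not defined, so exclusion is likely but not certain.
- *Voluntary exit from the pool:* Section 10.2 does not say whether this ends participation.

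The design is balanced. If that means each condition falls equally often at each visit, 18 completers give 18 / 3 = 6 control sessions and 12 baths at each of visits 2, 3 and 4. Of 36 planned baths, 24 fall at visit 2 or 3, where exclusion is certain, and 12 at visit 4, where it is only probable.

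**3. Whether any planned summary brings them back.** Section 13.2 does not. Section 13.3 covers missing data points, but 13.1 has already selected on completion. Section 13.5 covers early termination only. Outside Section 13, rectal temperature has an instruction, "For analysis, data will be grouped into 1 min average intervals" (10.1), and pool time is calculated (10.2), but neither is a count of stopped baths or withdrawals. Section 11.3 has adverse events recorded and all SAEs reported, with no tabulation.

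**4. Size under Section 8.** The documents give no rate of reaching a limit. Suppose 20 are recruited, 18 complete, and a person withdrawn at a limit does not count as completing. Some of the 2 losses may occur at visit 1, where there is an ECG review "where a clinical decision will be made on further participation to the study by consultants at QA hospital". Each condition is started by all 18 completers plus 0 to 2 others, so limit-triggered withdrawals within a condition cannot exceed starters minus 18. Clopper-Pearson 95% limits are the Beta quantiles B(0.025; x, n − x + 1) and B(0.975; x + 1, n − x):

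| Starters of a condition | Limit withdrawals | Proportion | Exact 95% CI |
|---|---|---|---|
| 20 | 0 | 0% | 0% to 16.8% |
| 20 | 1 | 5.0% | 0.1% to 24.9% |
| 20 | 2 | 10.0% | 1.2% to 31.7% |
| 19 | 0 | 0% | 0% to 17.6% |
| 19 | 1 | 5.3% | 0.1% to 26.0% |
| 18 | 0 | 0% | 0% to 18.5% |

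**5. Size without the cap of 2.** Assume that all 20 start, that limits are the only cause of loss, and that each person has probability p of withdrawal. The chance of at least one exclusion is 1 − (1 − p)^20, which is 0.64, 0.88 and 0.99 for p = 5%, 10% and 20%. The chance of more than two, leaving fewer than 18 completers, is 0.08, 0.32 and 0.79. All three values of p are assumptions.

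**6. What the collected data can support.**

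- *Blood pressure in condition 3.* The Figure 2 legend puts readings at 0830 and then from 1000. The OGTT starts at 1000, 30 minutes after a 60-minute bath, so the bath runs from 0830 to 0930. Apart from the baseline reading at its start, none is listed during it. The HR and BP paragraph of 9.4 says every 30 minutes, but less specifically.
- *Rectal temperature in the control condition.* Sections 6.3 and 9.4 have the thermistor in place at every experimental visit. Section 14 says it is inserted only at the two immersion visits.

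**The case against.** The strongest reply is that this is a reporting detail. Section 13.2 concerns endpoints, and stop counts are not endpoints. Adverse events are recorded and SAEs reported for everyone, total loss is visible as recruited minus analysed, and nothing prevents the sponsor from publishing a participant flow. All of that is true, and data capture is not the gap. But 13.1 is a stated rule, not a silence. Followed as written, it puts the limit-triggered withdrawals at visits 2 and 3 in no analysed set, and recording an event in a file does not give it a denominator, a condition or a reason.

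Four stronger readings are tempting, and the documents do not support them.

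- *Everyone who reaches a limit is certainly excluded.* Visit 4 is ambiguous, and Section 10.2 speaks only of leaving the pool.
- *The glucose AUC comparison is biased.* No rate of reaching a limit is given, and nothing links reaching one to glucose response.
- *The margins show that withdrawals will be common.* The target of 38.5°C is 0.5°C below the limit, but water cooling starts at about 38°C, which is 1.0°C below it. The blood pressure exclusion in 7.3 ("Uncontrolled hypertension", 180/100 or above) has the same value as the Section 14 limit, so someone just below it may enter. That says nothing about how often the limit is reached.
- *Safety events would go unreported.* Section 11.3 rules this out for SAEs.

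It also stands that a by-condition table needs by-condition denominators, and that some blood pressure and control-visit temperature readings may not exist. The proposed change allows for both.

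**Conclusion.** The point holds in a limited form. A person who reaches a limit at visit 2 or 3 is excluded from every planned analysis, one who first reaches it at visit 4 is probably excluded, and no planned summary includes either. Any cardiovascular or tolerability result from the 13.1 set would therefore describe mainly people who stayed within limits.

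The size is unknown. Under Section 8 it is at most 2 of 20 people, and intervals as wide as 1.2% to 31.7% mean that even a full count would be imprecise. The conclusion rests on 9.4, 10.1 and 14 governing over the softer wording of 10.2, which is reasonable because all three explicitly require withdrawal. The sample size is unaffected, and the primary result is not shown to be affected. The change should still be made, because the omission follows from a rule in the plan and is cheap to correct.

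**What to change.** - **Section 13.1.** Keep the completer set for the efficacy analysis. Add a safety set of everyone who starts any of visits 2 to 4, counted under each condition started, whether or not all visits are completed.
- **Section 13.2.** For that set, tabulate by condition, with the number starting that condition as denominator: immersions ended early and study withdrawals by reason (temperature, heart rate or blood pressure limit, own request, other), with exact 95% intervals; AEs and SAEs; pool time; peak heart rate; peak rectal temperature, for the control condition only if it is measured there; and the blood pressure readings actually taken. Include data up to the point of withdrawal.
- **Section 10.2.** Align the temperature wording with 9.4 and 10.1. State whether a voluntary early exit ends participation, and whether a limit reached at visit 4 counts as completion.

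The clinical limits and the sample size stay as they are. The cost is a few sentences and a few descriptive tables, with no new measurements or participants. The downside is imprecise proportions at about 20 people and possibly a less favourable safety statement.
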